6 STATISTICAL CONSIDERATIONS

6.1 Primary Endpoints

The primary efficacy endpoints will be the change in post-treatment Live and Virtual Police Interaction Assessment Scores between the Virtual Reality Intervention and treatment-as-usual groups, and the change in scores between the Baseline Assessment and Virtual Police Interaction Assessment.

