6.3.2 Efficacy Analysis

The primary analysis will be based on an intention to treat approach and will include all subjects randomized at Visit 1.

The primary efficacy endpoint will be the change in post-treatment Live Police Interaction Assessment Scores between the Virtual Reality Intervention and BE SAFE Video-Based intervention and the change in scores between the Baseline Assessment and Live Police Interaction Assessment. In the case of Cycle 2, the Baseline Assessment will be compared to the Virtual Police Interaction Assessment between the Virtual Reality Intervention and treatment-asusual groups. The study hypothesis is that participants randomly assigned to the Virtual Reality Intervention will perform better on the post-treatment Live or Virtual Police Interaction Assessment than will participants randomly assigned to the BE SAFE Video-Based intervention or treatment-as-usual condition.

The secondary endpoint will include changes in Police Interaction Knowledge Questionnaire Scores from Pre-Treatment to Post-Treatment for the Virtual Reality Intervention and BE SAFE Video-Based intervention or treatment-as-usual. The study hypothesis is that participants randomly assigned to the Virtual Reality Intervention will exhibit significantly greater improvement from Pre-Treatment to Post-Treatment on Police Interaction Knowledge Questionnaire than will participants randomly assigned to the BE SAFE Video-Based intervention condition or the treatment-as-usual condition. An additional Secondary endpoint is maintenance of learned skill improvements, indexed via the 4-week Follow-Up administration of the Virtual Police Interaction Assessment in Cycle B. The study hypothesis is that participants randomly assigned to the Virtual Reality Intervention will exhibit significantly greater Live Police Interaction Assessment Scores and skill improvement/maintenance 4-week follow-up than will participants randomly assigned to the treatment-as-usual condition.

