6.4 Sample Size and Power

This study will compare the PSM VR intervention to treatment-as-usual (TAU) in a total of 96 adolescents and adults with ASD, in two separate studies (i.e., n=48 per study). The most relevant study to date (Didehbani, Allen, Kandalaft, Krawczyk, & Chapman, 2016) included 30 7-16 year-olds with ASD in a pre/post virtual reality intervention to improve social cognitive skills. This study suggested a medium-to-large within-group effect of VR intervention on emotion recognition (Cohen's d = .63), but did not compare two interventions. Sensitivity analysis using G*Power indicated that intervention differences using our proposed sample size (N=48 per group) will be detected with a critical t of 1.99, and that we will be able to detect differences with effect sizes of Cohen's d = .74 or larger. Data will be behaviorally coded from video interactions and correct answers marked on knowledge tests. Scores will be summed, averaged, and examined for normality at the group level. Normally distributed data will be analyzed using parametric statistics (e.g., ANOVA, regression, Pearson correlation), and data that do not meet normality assumptions will either be transformed or will be analyzed using nonparametric statistical tests (e.g., Chi-square, Spearman correlation). Analyses will be corrected for comparisons. To compare PSM to BE SAFE, an Analysis of Variance (ANOVA) with Group (PSM VR Intervention, BE SAFE The Movie Video Modeling Intervention) as a Between-Subjects factor will be conducted for Live Interaction data. A separate ANOVA (or comparable statistical test) will be conducted for Questionnaire data. Relevant potential covariates include knowledge of police interactions at intake, sensory sensitivity scores, verbal abilities, and chronological age.

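### The Live half of the section 6.1 primary endpoint has no treatment-as-usual subjects and omits BE SAFE; section 6.3.2 pairs the arms correctly, but the Cycle B test and its status stay open

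*Combined protocol and SAP*

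**What the plan says.** **Section 6.1** gives two primary elements. The first is the "change in post-treatment Live and Virtual Police Interaction Assessment Scores between the Virtual Reality Intervention and treatment-as-usual groups". The second is "the change in scores between the Baseline Assessment and Virtual Police Interaction Assessment", with no group contrast named. BE SAFE does not appear.

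**Section 6.3.2** also gives two elements, but different ones. The first is the "change in post-treatment Live Police Interaction Assessment Scores between the Virtual Reality Intervention and BE SAFE Video-Based intervention". Its second element, again without a group contrast, reads "the change in scores between the Baseline Assessment and Live Police Interaction Assessment". For the other cycle it adds: "In the case of Cycle 2, the Baseline Assessment will be compared to the Virtual Police Interaction Assessment", between VR and TAU. The label Cycle 2 can only mean Cycle B. The stated hypothesis is that VR subjects "will perform better on the post-treatment Live or Virtual Police Interaction Assessment" than subjects in the relevant control.

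**Section 6.4** opens with "This study will compare the PSM VR intervention to treatment-as-usual (TAU) in a total of 96 adolescents and adults with ASD", divided into two studies of 48. Further down it specifies an ANOVA with "Group (PSM VR Intervention, BE SAFE The Movie Video Modeling Intervention) as a Between-Subjects factor will be conducted for Live Interaction data". It names no corresponding interaction-score test for Cycle B. It promises a correction for comparisons without giving the method or the family of tests.

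**Objectives.** The abstract makes VR versus video modeling primary and VR versus TAU secondary. Section 2.1 puts both in the primary objective. Section 2.2 lists VR versus TAU, delivered virtually, as secondary.

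**Baseline score.** Section 6.3.1 makes a baseline characteristic a covariate in the primary analyses if the groups differ on it significantly. Section 9.1.1 says much the same of variables that differ after randomization. The covariate list in 6.4 is open-ended and does not name the Baseline Assessment score.

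**The concern.** The section that should fix the primary endpoint names a comparison the design does not produce and leaves out one that it does. Read literally, 6.1 gives Cycle A no usable primary endpoint. An analyst must set 6.1 aside in favor of 6.3.2, and nothing in the plan says which section governs.

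Even then, choices remain that could be made after the data are seen: whether the baseline-to-post change is a second primary test, whether Cycle B is judged on the post score or on change, whether the baseline score is adjusted for, and whether the Cycle B result is primary. The last choice also decides which tests fall under the promised correction.

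**Working it through.** **1. Which subjects have which score.** Inputs: arms from 3.1.2 and 3.1.3; assessments from 5.4.2.1 and 5.4.2.2; separate populations from 9.6; about 48 evaluable subjects per cycle from 3.2.2 and 6.4.

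| | Cycle A | Cycle B |
|---|---|---|
| Arms | VR, BE SAFE video | VR, TAU |
| Visit 3 assessment | Live (real officer) | Virtual (avatar) |
| Subjects with a Live score | about 48 | 0 |
| Subjects with a Virtual score | 0 | about 48 |
| TAU subjects | 0 | about half of 48 if 1:1 (ratio not stated) |

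TAU subjects with a Live score: 0 in Cycle A (no TAU arm) + 0 in Cycle B (no Live assessment) = 0. Virtual, VR versus TAU, is computable in Cycle B. Live, VR versus BE SAFE, is computable in Cycle A, but 6.1 does not name it.

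**2. The sections side by side.**

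| Item | 6.1 | 6.3.2 | 6.4 |
|---|---|---|---|
| Control for Live | TAU | BE SAFE | TAU in the opening sentence, BE SAFE in the ANOVA |
| Baseline-to-post element | to Virtual | to Live | none |
| Cycle B test | Virtual, VR vs TAU | baseline compared with Virtual, between groups | none spelled out |

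VR versus TAU is primary in 2.1, 6.1 and 6.3.2, and secondary in the abstract and 2.2. TAU exists only in the virtual cycle, so 2.1 and 2.2 refer to the same comparison.

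**3. The plan's own figure.** Section 6.4 gives critical t = 1.99 and detectable d = .74 at 48 per group. With df = 94 and two-sided 0.05, critical t is 1.986. Noncentrality at d = 0.74 is 0.74 × √(48/2) = 3.63, and power is 94.8%. The figure therefore reproduces at about 95% power, which the plan does not state. It refers to 48 per group, whereas each cycle has 48 in total.

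**4. Illustration of what the choice of test does.** Assumptions not in the documents: 1:1 allocation (24 per arm), equal variances, a common scale for baseline and post, and baseline-post correlation ρ of 0.3, 0.5 or 0.7.

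- Post score: noncentrality 0.74 × √(24/2) = 2.56, df = 46, critical t 2.013, power 71%.
- Post score with baseline covariate: effective d = 0.74/√(1 − ρ²) = 0.776, 0.854, 1.036; df = 45; power 75%, 83%, 94% (noncentral-t approximation; simulation gave 74%, 82%, 93%).
- Change score: effective d = 0.74/√(2(1 − ρ)) = 0.625, 0.740, 0.955; df = 46; power 56%, 71%, 90%.

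**5. False-positive rate, conditional.** If the change element is a between-group test, and either it or the post-score test could be claimed at 0.05 with no correction, the two statistics correlate at √((1 − ρ)/2) = 0.592, 0.500, 0.387. The chance that at least one rejects under the null is 8.8%, 9.1%, 9.4% (bivariate normal).

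**The case against.** The best defense is that this is incomplete editing and that the intent is plain. Section 6.2, directly after 6.1, names both controls. Section 6.3.2 matches each control to its own assessment and states a directional hypothesis on the post-treatment score. Section 6.4 gives the Cycle A ANOVA against BE SAFE. For Cycle A this stands: the intended contrast is not in serious doubt. It does not settle Cycle B's test, the second primary element, or Cycle B's status.

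A reader might infer that the whole primary endpoint is uncomputable. The documents do not support that: the Virtual contrast and the baseline-to-Virtual change both have data. A reader might also try to rescue 6.1 by comparing Cycle A Live scores with Cycle B TAU scores. That comparison would be non-randomized and would use different assessments, and nothing in the plan proposes it.

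Nor may one say that the baseline score has no role. Section 6.3.1, with 9.1.1, arguably gives it a conditional one. The weakness is that the role depends on the observed data.

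The numbers in steps 4 and 5 are open to fair challenge. The change element names no group contrast and could be within-group, in which case the false-positive figures do not apply. Section 6.4 also promises a correction. The common-scale assumption is doubtful in Cycle A, where baseline is a role play with staff and the outcome an encounter with a real officer: with a baseline SD 1.5 times the post SD, change-score power would be 37%, 48% and 65%. Finally, 71% is low mainly because d = .74 was derived at 48 per group, which is a separate matter.

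**Conclusion.** The point holds in this form. The Live half of 6.1 has 0 TAU subjects and cannot be computed, and 6.1 omits Cycle A's only control. That conclusion rests on the design sections alone and needs no assumption. Cycle A's intended test is recoverable from 6.3.2 and 6.4, at the price of overriding 6.1. Unresolved from the text are the second primary element, the form of the Cycle B test, and whether VR versus TAU is primary or secondary. Whether the baseline score is adjusted for would be decided by a baseline significance test.

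The power and error figures are illustrations under the assumptions in steps 4 and 5. A reader might take 8.8% to 9.4% as the plan's error rate. The documents do not support that, because a correction is promised and the between-group reading of the change element is not stated.

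This should be fixed before analysis, because the defining statement of the primary endpoint is wrong as written.

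**What to change.** Rewrite 6.1, and align 6.3.2 and 6.4 with it, to one between-group primary test per cycle:

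- Cycle A: VR versus BE SAFE on the Visit 3 Live score.
- Cycle B: VR versus TAU on the Visit 3 Virtual score.

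Reconciling the sections is necessary. For the baseline element, the recommended choice is to enter the Baseline Assessment score as a prespecified covariate in each test, in place of the separate baseline-to-post primary element. In Cycle A a raw change score would mix the training effect with the change of setting.

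Consequential edits:

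- Amend 6.3.1 and 9.1.1 so that their difference-triggered rule does not govern the primary model.
- In 6.4, add the baseline covariate to the Live ANOVA, add a matching sentence for Cycle B, and name BE SAFE as the Cycle A control in the opening sentence.
- Give Cycle B one status in the abstract, 2.1, 2.2 and section 6.
- State which tests the 6.4 correction covers, and whether each cycle carries its own 0.05 claim or both share one. That is the sponsor's choice to state.
- In the 4-week hypothesis of 6.3.2, change Live to Virtual.

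Cost: amendment wording only if each cycle carries its own claim, since all the assessments are already scheduled. If one claim is shared and split at 0.025 per cycle, power at d = 0.74 without the covariate falls from about 71% to 60% at 24 per arm, under the same assumptions, unless more subjects are enrolled.

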5.3.2 Cycle B: Treatment-as-usual

Subjects assigned to the control condition will not receive any training with PSM, but will engage with the software for their assessments, and will continue their other treatments as usual. Participants in the treatment-as-usual arm will be screened for subject health status in preparation for their sessions.

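### For Cycle B, section 6.1 lists a baseline-to-post change with no arm comparison as a primary endpoint, section 6.3.2 compares that change between arms, and neither names the deciding contrast

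*Combined protocol and SAP*

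**What the plan says.** Section 6.1 uses the plural. Its first part is comparative: "The primary efficacy endpoints will be the change in post-treatment Live and Virtual Police Interaction Assessment Scores between the Virtual Reality Intervention and treatment-as-usual groups". It then adds "and the change in scores between the Baseline Assessment and Virtual Police Interaction Assessment" and names no arms. It gives neither a ranking nor a rule on whether one or both must succeed.

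Section 6.3.2, under the label Cycle 2 (read here as Cycle B), does bring in the arms: "the Baseline Assessment will be compared to the Virtual Police Interaction Assessment between the Virtual Reality Intervention and treatment-asusual groups". Its hypothesis then concerns the post-treatment score, not the change. It says that VR participants "will perform better on the post-treatment Live or Virtual Police Interaction Assessment than will participants randomly assigned to the BE SAFE Video-Based intervention or treatment-as-usual".

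Section 5.3.2 says that the Cycle B controls "will not receive any training with PSM, but will engage with the software for their assessments". Under 5.4.1.2 and 5.4.2.2 all participants have the VR-based assessment before the first session and again after the last one, and 3.1.3 describes it as a pre/post measure. The objectives in 2.1 and 2.2 are comparative. Section 6.4 promises a correction for multiple comparisons without giving a method. It specifies an ANOVA by group for the Live (Cycle A) data and no corresponding model for the Cycle B Virtual score.

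**The concern.** A reader who takes 6.1 and 6.3.2 together can extract three Cycle B contrasts: the post-treatment score between arms, the baseline-to-post change between arms, and the baseline-to-post change with no arms. The first two are both legitimate comparisons of the randomised groups, but they can give different answers and only one should decide.

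The third does not test the randomised treatment. If people simply do better the second time they meet a virtual officer in a headset, scores rise in both arms and the pre-post null hypothesis is false even when VR training adds nothing. Tightening alpha does not cure this, because the error lies in what is tested and not in how often. At stake is whether the trial could report a primary endpoint as met while the arms do not differ, when its objective is improvement relative to treatment-as-usual.

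**Working it through.** **Comparing the passages (Cycle B)**

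| Place | Quantity | Arms compared? |
|---|---|---|
| 6.1, first part | Post-treatment score | Yes |
| 6.1, second part | Baseline-to-Virtual change | Not stated |
| 6.3.2, Cycle 2 sentence | Baseline-to-Virtual change | Yes |
| 6.3.2, hypothesis | Post-treatment score | Yes |
| 2.1 and 2.2, objectives | Improvement relative to control | Yes |

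No row is marked as decisive anywhere in the document.

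**The plan's own figure.** Section 6.4 gives a critical t of 1.99 and a detectable d of 0.74 with 48 per group. A two-sided 5% t-test with 94 degrees of freedom has critical t 1.986, and d = 0.743 is detectable at 95% power (a power the plan does not state). This supports two-sided 5% as the intended level. Section 6.4 also says 48 per study. I use 24 per arm, assuming 1:1 allocation, which is not stated.

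**Retest illustration.** Assumptions not found in the documents: a gain g in SD units, equal in both arms; no VR effect; baseline-post correlation r; and a paired t-test, which the plan does not specify.

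- Standardised change: dz = g / √(2(1 − r)). With g = 0.3, dz is 0.254, 0.300 and 0.387 at r = 0.3, 0.5 and 0.7.
- Noncentrality: dz × √n. At r = 0.5 this is 0.300 × √24 = 1.47 and 0.300 × √48 = 2.08.
- Critical t at two-sided 5%: 2.069 (23 df) and 2.012 (47 df).
- Chance of a significant gain, from the noncentral t:

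| g = 0.3 | r = 0.3 | r = 0.5 | r = 0.7 |
|---|---|---|---|
| VR arm, n = 24 | 0.22 | 0.29 | 0.44 |
| All subjects, n = 48 | 0.41 | 0.53 | 0.75 |

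At r = 0.5, a gain of 0.2 SD gives 0.15 and 0.27, and a gain of 0.5 SD gives 0.65 and 0.92. Testing at 0.025 with g = 0.3 and r = 0.5 still gives 0.20 and 0.41.

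In the between-arm comparison the common gain cancels. In 40,000 simulated trials per setting, rejection stayed at about 0.05 two-sided (0.025 in favour of VR) at every gain tried.

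**Choice of the deciding contrast.** Take d = 0.74, 24 per arm, two-sided 5%. The noncentrality for the unadjusted post score is 0.74 × √12 = 2.563. Divide it by √(2(1 − r)) for the change score and by √(1 − r²) for the baseline-adjusted score (45 df).

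| Power | r = 0.3 | r = 0.5 | r = 0.7 |
|---|---|---|---|
| Visit 3 score, unadjusted | 0.71 | 0.71 | 0.71 |
| Change score | 0.56 | 0.71 | 0.90 |
| Visit 3 score, baseline-adjusted | 0.75 | 0.83 | 0.94 |

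The adjusted comparison has the highest power at each correlation.

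**The case against.** The strongest reply is that 6.1 is only a list and 6.3.2 is the analysis. Section 6.3.2 supplies the missing arms, and both objectives are comparative. The list in 6.2 is equally terse about 4-week maintenance, and 6.3.2 then gives that endpoint a between-arm hypothesis too. On this view the second clause of 6.1 abbreviates the comparison in 6.3.2. No passage says that a change tested against zero counts as success, so the paired test is the reviewer's construction.

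Most of this stands. The between-arm reading is the more plausible one, and the retest probabilities apply only if it is rejected. What the reply does not settle is the choice between post score and change, since 6.3.2 itself uses both. Nor does 6.3.2 say that it replaces 6.1. It also repeats the form without arms for Cycle A ("and the change in scores between the Baseline Assessment and Live Police Interaction Assessment"), so the wording in 6.1 is not an isolated slip.

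A reader might make two stronger inferences. One is that the plan as a whole leaves the Cycle B change uncontrolled; 6.3.2 contradicts that. The other is that having two between-arm contrasts inflates false success to about 0.09. That figure counts rejections in either direction, before the correction that 6.4 promises. Rejections in favour of VR, the stated hypothesis, come to about 0.045, and testing each contrast at 0.025 brings the two-directional rate to about 0.05 or slightly below. The figure does not support a claim of inflated success.

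**Conclusion.** The concern holds as a conflict between 6.1 and 6.3.2 with no named deciding contrast for Cycle B. It does not show that the plan intends an uncontrolled pre-post test.

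If 6.1 were followed to the letter, retest gain alone could meet a primary endpoint. The illustrative probabilities of 0.29 (VR arm) and 0.53 (all subjects) rest on four conditions: the literal reading, an unspecified paired test, 24 per arm, and an assumed 0.3 SD gain with correlation 0.5. The documents give no retest gain, so these figures show that the risk could be material. They do not estimate its size in this trial. The wording should be settled before the Cycle B data are analysed.

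**What to change.** In 6.1, replace the clause that names no arms with a between-arm comparison, and state the same single deciding Cycle B contrast in 6.1 and 6.3.2: the VR minus treatment-as-usual difference in the Visit 3 Virtual Police Interaction Assessment score, adjusted by ANCOVA for the Cycle B Baseline Assessment score, two-sided 5%. State that within-arm pre-post change is descriptive and that no efficacy claim rests on it.

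The baseline score is already collected, although 6.4 does not name it among the potential covariates. Adjusting for it keeps the use of baseline that 6.3.2 plans, and does not require the two assessments to be scored on the same scale.

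The cost is wording in two sections, with no new data or subjects. The sponsor gives up pre-post change as a primary claim but can still report it.

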6.2 Secondary Endpoints

Secondary endpoints will include the following:

- The changes in Police Interaction Knowledge Questionnaire Scores from Pre-Treatment to Post-Treatment for the Virtual Reality Intervention and BE SAFE Video-Based intervention or treatment-as-usual:
- The maintenance of learned skill improvements, indexed via the 4-week (Cycle B) Follow-Up administration of the Virtual Police Interaction Assessment.

6.3 Statistical Methods

6.3.1 Baseline Data

Baseline and demographic characteristics will be summarized by standard descriptive summaries (e.g., means and standard deviations for continuous variables such as age and percentages for categorical variables such as gender). Statistical analyses will be conducted to compare groups on each of the measures. Any baseline characteristics which exhibit statistically significant group differences despite stratified random assignment will be utilized as co-variates in both Primary and Secondary statistical analyses of intervention effects.

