3.3 Study Population

3.3.1 Inclusion Criteria

- 1) Males or females age 12 to 60 years
- 2) Documented ASD diagnosis
- 3) Verbal and overall IQ \geq 75 (Cycle A)/Verbal and overall IQ \geq 80 (Cycle B)
- 4) Informed consent (if adult) or parental/guardian permission (if child or adult with diminished capacity) and, if applicable, assent

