5.1.4 Autism Screening

Social Communication Questionnaire (SCQ; Rutter, Bailey, & Lord, 2003). The SCQ is a parent report screening measure for ASD that has been validated for identifying children displaying autism symptoms. The SCQ will be completed by parents of participants.

Autism-Spectrum Quotient (AQ; (Ruzich et al., 2015)). The AQ is a widely used, 50-item self-report questionnaire designed to measure reciprocal behavior, social use of language, and other behaviors characteristic of ASD. Total AQ score and 5 subscales (communication, social skills, imagination, attention to detail, attention switching) are normally distributed, demonstrate good test-retest reliability, and have medium-to-high internal consistency (Baron-Cohen, Wheelwright, Skinner, Martin, & Clubley, 2001).

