5.1.5 Other Measures and Questionnaires

Adult/Adolescent Sensory Profile (Brown, et al., 2001). The Adolescent/Adult Sensory Profile is designed as a trait measure of sensory processing patterns and effects on functional performance. An individual answers questions regarding how he or she generally responds to sensations, as opposed to how he or she responds at any given time. This enables the instrument to capture the more stable and enduring sensory processing preferences of an individual.

Child Behavior Checklist (CBCL) OR Adult Behavior Checklist, (T. Achenbach & Rescorla, 2001). The CBCL is a 118-item checklist completed by parents regarding a broad range of behavioral and emotional problems. Statements are rated from 0 to 2 based on how well the statement describes the youth: 0 (not true), 1 (somewhat or sometimes true) and 2 (very often true). Scores are reported for both internalizing and externalizing scales including the following subscales: Anxious/Depressed, Withdrawn/Depressed, Somatic Complaints, Social Problem, Thought Problems, Attention Problems, Rule-Breaking Behavior, and Aggressive Behavior. The Adult Behavior Checklist is a parent-report extension of the CBCL intended for adults aged 18-59. The Adult Self-Report is the self-report extension of the CBCL intended for adults aged 18-59.

Social Responsiveness Scale – Second Edition (SRS-2; Constantino, 2012). The SRS-2 distinguishes autism spectrum conditions from other psychiatric conditions by identifying presence and extent of autistic social impairment. The SRS-2 is a 65-item quantitative measure of autistic traits ranging continuously from significantly impaired to above average. Familial correlations of sub-clinical features of autism can be measured by the SRS-2, which is consistent with the potential for heritability of a broad autism phenotype in family members. Parents will complete the SRS-II or the SRS-ARV, as appropriate to the participant's age, as the measure of autistic traits in non-ASD and ASD participants. The SRS-2 will be completed by parents of subjects age 12-17.

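### The open, mandatory covariate rule in 6.3.1 can select measures not available for every randomised subject aged 12 to 60, and no handling of missing covariates is stated

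*Combined protocol and SAP*

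**What the plan says.** Section 6.3.1 sets the pool and the rule. On the pool: "Statistical analyses will be conducted to compare groups on each of the measures". On the rule: "Any baseline characteristics which exhibit statistically significant group differences despite stratified random assignment will be utilized as co-variates in both Primary and Secondary" analyses. Section 9.1.1 adds that variables found to differ after stratified randomisation will be dealt with statistically in the primary analyses. Neither section closes the list.

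Eligibility is "Males or females age 12 to 60 years" (3.3.1). Against that range:

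- **SRS-2 (5.1.5).** One sentence reads "The SRS-2 will be completed by parents of subjects age 12-17". Another in the same paragraph reads "Parents will complete the SRS-II or the SRS-ARV, as appropriate to the participant's age", which sets no upper age.
- **Behaviour checklists (5.1.5).** Minors have the CBCL. For adults, "The Adult Behavior Checklist is a parent-report extension of the CBCL intended for adults aged 18-59". The Adult Self-Report covers the same adult ages; no self-report counterpart for minors is described.
- **SCQ (5.1.4).** "The SCQ will be completed by parents of participants", with no age limit.

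Section 6.3.2 makes the primary analysis intention to treat: it "will include all subjects randomized at Visit 1". Section 6.4 names ANOVA and regression as the parametric methods. It lists four potential covariates: intake knowledge, sensory sensitivity, verbal ability and chronological age. Nothing in the document says what happens when a covariate value is missing.

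**The concern.** The rule is compulsory, and it can pick a measure that part of the sample does not have by design. ANOVA and regression routines by default keep only subjects with every covariate present. If such a measure triggers, the analyst cannot follow 6.3.1 with the methods of 6.4 and still include everyone as 6.3.2 requires, unless a rule is made up after the baseline comparisons are known.

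Two things are at stake. The first is precision, because each cycle is small. The second is whom the result describes: with the SRS-2 on its narrow reading the analysed set would be minors, and with the Adult Self-Report it would be adults.

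This differs from the general question of whether a significance test should decide adjustment. It concerns what is allowed into the pool, and it would remain under any other data-driven selection rule that left the pool open.

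**Working it through.** **1. The plan's own figure.** Section 6.4 gives a critical t of 1.99 and a detectable d of 0.74 with 48 per group. For a two-sample t-test at two-sided 5%, power = P(T > t(0.975, df)), where T is noncentral t with noncentrality d × √(n/2), n is per arm and df = 2n − 2. The negligible opposite tail is ignored.

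- n = 48: t(94) = 1.986. Detectable d is 0.578 at 80% power, 0.669 at 90% and 0.743 at 95%. The plan's 0.74 is reproduced at 95% power, which the plan does not state.
- n = 24: t(46) = 2.013. Detectable d is 0.826 at 80% and 1.063 at 95%.

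Section 6.4 also says 48 per study, in two separate studies. At 1:1 (the ratio is not stated) that is 24 per arm, and this is the basis used below.

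**2. Who has each measure.**

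| Measure | Availability as written | Gap in a 12 to 60 sample |
|---|---|---|
| SRS-2 | 12 to 17 by one sentence; age-appropriate form by another | All adults, or none, depending on which sentence governs |
| Adult Self-Report | 18 to 59 | Minors, and age 60 |
| CBCL / Adult Behavior Checklist | Parent report; adult form 18 to 59 | Age 60, adults without a parent informant; two forms with no common scale stated |
| SCQ | Parent report, any age | Adults without a parent informant |

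The documents give neither the age split nor the number of adults with a parent informant.

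**3. Chance of a trigger.** Under randomisation, with k independent baseline tests at 5% (an assumed level; 6.3.1 gives none), P(at least one) = 1 − 0.95^k.

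- k = 1: 5.0%
- k = 3: 1 − 0.857 = 14.3%
- k = 5: 22.6%
- k = 10: 40.1%

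Reaching k = 10 means counting subscales. Those are likely to be correlated, which lowers the figure. It would also be lower if the correction for comparisons mentioned in 6.4 applied to baseline tests, which is not said.

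**4. Loss if a partly available measure triggers.** Complete-case model, one covariate, df = 2n − 3, no precision gain from the covariate, shares with the form assumed and equal between arms:

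| Share with form | Per arm | Lost of 48 | Detectable d, 80% power | Power at d = 0.74 |
|---|---|---|---|---|
| 100% | 24 | 0 | 0.83 | 71% |
| 75% | 18 | 12 | 0.96 | 58% |
| 50% | 12 | 24 | 1.20 | 41% |
| 25% | 6 | 36 | 1.82 | 21% |

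If 48 per arm was meant, the same shares give 0.58, 0.67, 0.83 and 1.20.

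**5. Could the covariate pay for the loss?** A covariate with correlation r to the outcome multiplies the detectable d by about √(1 − r²). To offset the fall to 50%, √(1 − r²) must be 0.827/1.200 = 0.689, so r² = 1 − 0.475 = 0.525 and r is about 0.72. The documents give no correlation from which to judge whether that is realistic.

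**The case against.** The strongest reply is that the plan nowhere orders a complete-case analysis. Section 6.3.2 commits to the opposite set, and 6.4 leaves room for a comparable test. That stands: the exclusion is the default of the named methods, not an instruction. What remains is that the plan offers no other handling.

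A reader might infer that an SRS-2 imbalance would certainly remove all adults. The documents do not support that, because the SRS-II/SRS-ARV sentence in 5.1.5 implies that adults have a form too. The two sentences conflict and need reconciling. Even on the wider reading, two forms need a rule before they can serve as one covariate.

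A reader might also take the parent-report forms to be age-limited as a group. They are not. The SCQ has no age limit, and the checklists have an adult counterpart up to 59. Their gap is adults without a parent informant. Section 5.2 involves parents only where appropriate, so some such adults are possible, but no figure shows that they are many.

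Section 6.4 names potential covariates that are not described as age-limited, and 5.1.5 enters demographic and history items only for imbalance on critical features. Both make an SRS-2-driven model less likely. Neither overrides 6.3.1: the first list is introduced as an inclusion, and the second concerns one form.

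Finally, it can be said that the problem arises only through the significance trigger, so that one repair cures both. That is largely right about the repair. A fixed list still needs to be limited to variables that everyone has, and it still needs a missing-value rule.

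**Conclusion.** The point holds as a conditional conflict between 6.3.1 (with 9.1.1) and 6.3.2. An open, compulsory rule can bring in a measure that part of the sample lacks, and the plan states no handling that keeps everyone in the model.

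For any one measure the chance is about 5% per cycle. It is higher across several measures, but below the independent-test figures if they are correlated. If it happens and the model is complete-case, detectable d at 80% power goes from 0.83 to about 0.96, 1.20 or 1.82 at 75%, 50% or 25% availability. This assumes 24 per arm at 1:1, one covariate and no precision gain; the shares are not in the documents.

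It would be wrong to set the 14% to 40% chance for 3 to 10 scales beside the loss of all adults. That loss belongs to the SRS-2 alone, at about 5%, and only on the narrow reading of 5.1.5. Nor do the documents show that the comparison would be biased. Where availability follows age alone it is fixed before randomisation, so the harm is lost subjects and a narrower population. The change is worth making because it is cheap and protects the stated analysis set.

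**What to change.** In 6.3.1, replace the open rule with a fixed covariate list for the primary and secondary models, made up of variables collected from every randomised subject before treatment:

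- chronological age and sex;
- verbal IQ, from the WASI-II or the equivalent test used (5.1.2 allows either);
- the pre-treatment score of the outcome: Baseline Assessment or pre-treatment knowledge score;
- the sensory score, only if completed before the first session, since Table 1 spreads questionnaires over Visits 1 to 3 (and Visit 4 in Cycle B).

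State that SRS-2, SCQ, CBCL, Adult Behavior Checklist and Adult Self-Report are descriptive only. State also that a sporadically missing value of a listed covariate is singly imputed from baseline data, without using treatment arm, so that all randomised subjects stay in the model. Align 9.1.1, and reconcile the two SRS sentences in 5.1.5.

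The cost is a few sentences and no new data. The downside is that a chance imbalance on a parent-report trait scale would be described and not adjusted for.
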